7. STUDY EVALUATIONS

7.1. Time and Event Schedule

Table 5: Time and Events

Visit Information	Visit 1 Baseline, Dispense Washout lenses	Visit 2 Study lens pair #1 fitting and follow-up after 45 min	Visit 3 Study lens pair #2 fitting and follow-up after 2 hours	Visit 4 Study lens pair #3 fitting and follow-up after 45 min	Visit 5 Study lens pair #4 fitting and follow-up after 2 hours
Time Point		5-7 days after V1	5-7 days after V2	5-7 days after V3	5-7 days after V4
Estimated Visit Duration	2 hours	2 hours	3 hours	2 hours	3 hours
Study Informed Consent	X				
Inclusion/Exclusion Screening Criteria	X				
Demographics	X				
Medical History & medication review	X	X	X	X	X
Modified CLDEQ-8	X	X	X	X	X
Habitual Lens Info	X				
Keratometry	X				
Subjective Refraction	X				
Eye Dominance	X				
Baseline Biomicroscopy	X	X	X	X	X
Baseline expanded corneal staining	X	X	X	X	X
Eligibility	X				

Visit Information	Visit 1 Baseline, Dispense Washout lenses	Visit 2 Study lens pair #1 fitting and follow-up after 45 min	Visit 3 Study lens pair #2 fitting and follow-up after 2 hours	Visit 4 Study lens pair #3 fitting and follow-up after 45 min	Visit 5 Study lens pair #4 fitting and follow-up after 2 hours
Time Point		5-7 days after V1	5-7 days after V2	5-7 days after V3	5-7 days after V4
Estimated Visit Duration	2 hours	2 hours	3 hours	2 hours	3 hours
Randomization	X				
Washout Lens fitting	X				
Lens pair #1 fitting (Washout)		X			
Lens pair #2 fitting			X		
Lens pair #3 fitting				X	
Lens pair #4 fitting					X
Snellen VA	X	X	X	X	X
Ocular Symptoms	X	X	X	X	X
Post fit VAS comfort	X				
1 min post fit VAS comfort		X	X	X	X
5 min post fit VAS comfort		X	X	X	X
45 min post fit VAS comfort			X		X
Lens Fit Assessment	X	X	X	X	X
Lens Surface Assessment	X	X	X	X	X
Lens Deposits Assessment	X	X	X	X	X
Lens Dispensing & Instruction	X	X	X	X	
Wear Time		X	X	X	X
45-minute follow-up VAS comfort		X		X	
120-minute follow-up VAS comfort			X		X
Follow-up Ocular symptoms		X	X	X	X
Follow-up lens fit		X	X	X	X
Follow-up lens surface assessment		X	X	X	X
Exit Slit-lamp		X	X	X	X
Exit Expanded Corneal staining		X	X	X	X
Adverse Event Review		X	X	X	X
Final Evaluation					X

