2.14.	Subjective Lens Fit Assessment	Evaluate overall lens fit acceptance (acceptable or unacceptable) based on centration, movement and other fitting characteristics. An unacceptable fit is deemed by one of the following criteria: 
 • limbal exposure at primary gaze or with extreme eye movement • edge lift • excessive movement in primary and up gaze • insufficient movement in all three of the following conditions: primary gaze, up gaze, and Josephson push up Note: if lens fit is unacceptable subject will be discontinued from the study.
2.15.	White Light Lens Surface Wettability	Record the white light lens wettability of both lenses.

Visit 2: Lens pair #1 Fitting		
Step	Procedure	Details
2.16.	Surface Deposits	Record any front and back surface lens deposits.
2.17.	Continuance	
For the subject to continue in the study, they must meet all three of the following criteria:
 
 • Visual acuity is 20/30 or better OD and OS • The lens fit is acceptable OD and OS • Investigator approval. 
If the Investigator does not approve the dispensing of the first study lens, then the study is terminated for that subject.

2.18.	Wear time - 45 minutes	
Subjects will wear the study lenses (in office) for 45 minutes.
 
During this time, no rewetting drops are permitted.
 
Note: no lenses will be replaced during the wear time. If a new lens is needed, the visit will be stopped, an exit slit lamp and visual acuity will be completed and the subject will be discontinued from the study.

Visit 2: Lens Pair #1 Follow-Up		
Step	Procedure	Details
2.19.	Compliance	Confirm compliance with the prescribed wear schedule.
2.20.	45-minute Follow-Up VAS Questionnaires	The subject will respond to the Follow-Up VAS Questionnaires.
2.21.	Subject Reported Ocular Symptoms	Subjects will respond to a verbal open-ended symptoms questionnaire.
2.22.	Visual Acuity	Record the distance Snellen visual acuity with the study CLs (OD, OS, and OU) to the nearest letter. Subjects must read the smallest line until at least 50% of the letters are read incorrectly.
2.23.	Subjective Lens Fit Assessment	Evaluate overall lens fit acceptance (acceptable or unacceptable) based on centration, movement and other fitting characteristics.

Visit 2: Lens Pair # 1 Follow-Up		
Step	Procedure	Details

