3.14.	Subjective Lens Fit Assessment	
Evaluate overall lens fit acceptance (acceptable or unacceptable) based on centration, movement and other fitting characteristics.
 
An unacceptable fit is deemed by one of the following criteria:
	

Visit 3, Lens pair #2 Fitting		
Step	Procedure	Details
		
 • limbal exposure at primary gaze or with extreme eye movement • edge lift • excessive movement in primary and up gaze • insufficient movement in all three of the following conditions: primary gaze, up gaze, and Josephson push up 
Note: if lens fit is unacceptable subject will be discontinued from the study.

3.15.	White Light Lens Surface Wettability	Record the white light lens wettability of both lenses.
3.16.	Surface Deposits	Record any front and back surface lens deposits.
3.17.	Continuance	
For the subject to continue in the study, they must meet all three of the following criteria:
 
 • Visual acuity is 20/30 or better OD and OS • The lens fit is acceptable OD and OS • Investigator approval. 
If the Investigator does not approve the dispensing of the first study lens, then the study is terminated for that subject.

3.18.	Wear time- 120 minutes	
Subjects will wear the study lenses (in office) for 120 minutes.
 
During this time, no rewetting drops are permitted.
 
Note: no lenses will be replaced during the wear time. If a new lens is needed, the visit will be stopped, an exit slit lamp and visual acuity will be completed and the subject will be discontinued from the study.

3.19.	45-minute Post-Fit VAS Questionnaire	The subject will respond to the Post-Fit VAS Questionnaire.

Visit 3: Lens Pair # 2 Follow-Up		
Step	Procedure	Details
3.20.	Compliance	Confirm compliance with the prescribed wear schedule.
3.21.	120-minute Follow-Up VAS Questionnaires	The subject will respond to the Follow-Up VAS Questionnaires.
3.22.	Subject Reported Ocular Symptoms	Subjects will respond to a verbal open-ended symptoms questionnaire.
3.23.	Visual Acuity	Record the distance Snellen visual acuity with the study CLs (OD, OS, and OU) to the nearest letter. Subjects must read the smallest line until at least 50% of the letters are read incorrectly.

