14. STATISTICAL METHODS

14.1. General Considerations

Statistical Analysis will be undertaken by the sponsor or under the authority of the sponsor. A general description of the statistical methods to be implemented in this clinical trial is outlined below.

All data summaries and statistical analyses will be performed using the SAS software Version 9.4 or higher (SAS Institute, Cary, NC). Throughout the analysis of data, the results for each subject/eye will be used when available for summarization and statistical analysis. Unscheduled visits will be summarized separately.

Summary tables (descriptive statistics and/or frequency tables) will be provided for all baseline variables, efficacy variables and safety variables as appropriate. Continuous variables will be summarized with descriptive statistics (n, mean, standard deviation [SD], median, minimum and maximum). Frequency count and percentage of subjects or eyes within each category will be provided for categorical data.

Summaries will be presented by study solution, by lens type and across all lens types.

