14.2. Sample Size Justification

This is a pilot study and the sample size was not based on any empirical power calculation. The collected data will be used to design future clinical evaluation.

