14.5. Primary Analysis

Initial comfort scores at 1-min, 5-min, 45-min and 2-hour post-fit will be analyzed using a multivariate hierarchical Bayesian model for repeated measures to test for the difference between the test solution and control solutions at 1-min, 5-min, 45-min and 120-min. The regression model will include sequence, period, solution, lens and lens by solution interaction as fixed effects. Investigational site, subjects and eye nested within subjects will be included as random effect factors.

The Model:

Let $\mathbf{y}_{ijk} = (y_{1ijk}, y_{2ijk}, y_{3ijk}, y_{4ijk})$ denote the initial comfort scores for the i^{th} eye of the j^{th} subject, from k^{th} site at 1-min, 5-min, 45-min and 2-hour post fit. The likelihood of \mathbf{y}_{ijk} is constructed as follow:

$$\mathbf{y}_{ijk} \sim N(\boldsymbol{\mu}, \boldsymbol{\Sigma}),$$

where $\boldsymbol{\mu} = (\mu_1, \mu_2, \mu_3, \mu_4)^T$ and $\boldsymbol{\Sigma}$ is a 4×4 variance-covariance matrix. Here μ_1, μ_2, μ_3 and μ_4 are given by:

$$\mu_i = \mu_0 + \beta_1 \text{sequence} + \beta_2 \text{period} + \beta_3 \text{lens} + \beta_4 \text{solution} + \beta_5 \text{lens*solution} + \delta_{i(jk)} + \delta_{j(k)} + \delta_k,$$

where $\delta_{i(jk)} \sim N(0, \sigma_{\text{eye}}^2)$, $\delta_{j(k)} \sim N(0, \sigma_{\text{subj}}^2)$, $\delta_k \sim N(0, \sigma_{\text{site}}^2)$. Other baseline characteristics such as age, gender and CLDEQ-8 score will also be included as fixed effects when appropriate.

Non-informative prior distributions will be used for the coefficients in the models as well as for the error terms: Independent vague normal $N(0, 1000)$ priors for the regression coefficients (μ_0 and $\boldsymbol{\beta}$), inverse gamma $IG(0.001, 0.001)$ for $\sigma_{\text{eye}}^2, \sigma_{\text{subj}}^2, \sigma_{\text{site}}^2$ and inverse Wishart $IW(R, 4)$ for $\boldsymbol{\Sigma}$. R is determined by $S = E[\boldsymbol{\Sigma}] = 4R$ where S is the sample variance-covariance matrix of the \mathbf{y}_{ijk} . The Metropolis sampler algorithm as implemented in the MCMC Procedure (SAS 9.4, SAS Institute, Cary, NC) will be used to estimate the posterior distributions of the unknown parameters. Inferences will be made based on a posterior credible interval for the relevant parameters. Results will be reported as regression coefficient mean estimates with 95% credible intervals.

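### The primary model has no visit index and no visit-specific term shared by the two eyes, so the same-visit pairing of test and control enters only through an overall subject effect, and no rule places 14 scores per eye in four slots

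*Combined protocol and SAP*

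**What the plan says.** All references are to the combined protocol and SAP.

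- **Model (Section 14.5).** The response is a four-slot vector (1, 5, 45 minutes, 2 hours) indexed by eye, subject and site. Fixed effects are sequence, period, solution, lens and lens by solution. For the random part, "Investigational site, subjects and eye nested within subjects will be included as random effect factors". The 4×4 residual matrix covers the four times of one eye.
- **Schedule (Section 7.1, Table 5; Section 7.2).** The row "1 min post fit VAS comfort" is ticked at Visits 2 to 5, as is the 5-minute row. The 45-minute score is taken at Visits 2 and 4 as "45-minute Follow-Up VAS Questionnaires" and at Visits 3 and 5 as "45-minute Post-Fit VAS Questionnaire". The "120-minute Follow-Up VAS Questionnaires" appear at Visits 3 and 5 only.
- **Data use (Section 14.1).** The plan says "the results for each subject/eye will be used when available for summarization and statistical analysis" and "Summaries will be presented by study solution, by lens type and across all lens types".
- **Design reason (Section 4.2).** The contralateral design was chosen because it controls patient factors such as tear film quality.
- **Eye allocation.** Section 5.1 randomises test and control to left and right eyes without saying whether Period 2 has a new draw.
- **Purpose.** Section 2.3 calls the study an exploratory pilot. Section 14.2 gives no power basis and adds: "The collected data will be used to design future clinical evaluation".

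**The concern.** The benefit of a contralateral design comes from comparing two eyes on the same day. If a subject's eyes are both drier or more irritable at one visit, that shift cancels from test minus control. The planned model has nowhere to put such a shift. It spreads it over the subject, eye and residual variances, and so treats part of it as independent error in each eye. The intervals then become wider than the design allows.

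The scores also do not fit the vector. Each period has two visits with the same solution pair, so the 1-, 5- and 45-minute slots are filled twice. Two analysts following Section 14.5 could stack, average or select visits and report different primary intervals.

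The practical stake is the next study. A contralateral successor would be sized on the variance of the within-visit difference. Neither the planned model nor the by-solution summaries report it.

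**Working it through.** **Count of scores.** Visits 2 and 4 give 3 scores per eye each, and Visits 3 and 5 give 4 each: 2×3 + 2×4 = 14 per eye, or 7 per period. The vector as indexed has 4 slots, or 8 if a period index is added.

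**Inputs.** The plan states no effect size, SD or power, so there is no figure to reproduce. The 90 completers come from Section 4.3. All variances are assumptions: subject 150, eye e = 20, residual r = 100, shared visit v = 50 or 100, no subject-by-solution variance. One time point is taken alone, with its own solution effect, in large samples. Site and subject effects cancel from the comparison.

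**Formulas.** Let m be the visits used per period: 2 if all are stacked, 1 if only Visits 3 and 5. Per subject, put P = r/m, Q = 2e + r/m, U = (2v + r)/m. CLEAR CARE minus test equals A − B, where A is the mean of the two controls minus test, and B is half of OPTI-FREE minus CLEAR CARE.

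- Test eye fixed: information on A is 1/Q; on B it is 1/P + 1/U.
- Test eye re-drawn (half the subjects switch): information on A is (1/P + 1/Q)/2; on B it is (1/P + 1/Q)/2 + 1/U.
- Variance = 1/info(A) + 1/info(B); divide by 90 and take the root for the SE.

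The planned model uses the same formulas with v = 0 and its best-fitting values r′ = r + v and e′ = e − v/(2m). If e′ would be negative, it is 0, and r′ = [3(2v+r) + 3r + (4e+r)]/7 (stacked) or [(2v+r) + r + (2e+r)]/3 (Visits 3 and 5).

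**One case in full (stacked, re-drawn, v = 50).** With the term: P = 50, Q = 90, U = 100. Info(A) = 0.015556, giving 64.29. Info(B) = 0.025556, giving 39.13. The sum is 103.42. Planned: r′ = 150, e′ = 7.5, so P = U = 75 and Q = 90. Info(A) = 0.012222, giving 81.82. Info(B) = 0.025556, giving 39.13. The sum is 120.95. SE ratio: √(120.95/103.42) = 1.08.

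**All cases.** The third variance column is the actual variance of the planned estimator (its weights, the true variances). Coverage is 2Φ(1.96√(reported/actual)) − 1.

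| Visits used | Test eye | v | Planned, reported | With term | Planned, actual | SE ratio | Coverage |
|---|---|---|---|---|---|---|---|
| All | re-drawn | 50 | 120.95 | 103.42 | 109.48 | 1.08 | 96.1% |
| All | re-drawn | 100 | 147.86 | 109.29 | 125.00 | 1.16 | 96.7% |
| All | fixed | 50 | 127.50 | 123.33 | 127.50 | 1.02 | 95.0% |
| All | fixed | 100 | 147.86 | 127.50 | 140.00 | 1.08 | 95.6% |
| 3 and 5 | re-drawn | 50 | 220.00 | 190.35 | 200.00 | 1.08 | 96.0% |
| 3 and 5 | re-drawn | 100 | 270.00 | 200.67 | 225.00 | 1.16 | 96.8% |
| 3 and 5 | fixed | 50 | 220.00 | 206.67 | 215.00 | 1.03 | 95.3% |
| 3 and 5 | fixed | 100 | 270.00 | 215.00 | 240.00 | 1.12 | 96.2% |

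At v = 0 every ratio is 1.

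**Effect of the missing repeat rule.** Stacking rather than using Visits 3 and 5 alone narrows the planned interval by 1 − √(120.95/220) = 26% (re-drawn) or 1 − √(127.5/220) = 24% (fixed) at v = 50.

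**Planning variance.** The true one-visit paired variance is 2(e + r) = 240. The planned fit implies 2(e′ + r′). Stacked, this is 315 at v = 50 and 394 at v = 100, or 1.31 and 1.64 times the true value. For Visits 3 and 5 it is 293 and 360, or 1.22 and 1.50 times.

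**The case against.** **The eyes are already linked.** A reader might infer that the model ignores the pairing altogether. It does not: the subject effect is common to both eyes and removes stable differences between people. Only the visit-specific link is missing.

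**The intervals might be thought too narrow.** With all visits stacked and the test eye re-drawn, coverage of 85.6–91.7% can be produced. That result arises at zero visit variance, where a missing visit term costs nothing. It comes from an assumed subject-by-solution variance of 25–50, which is a separate omission. With a fixed test eye and stacked visits, coverage under that assumption is 93.8–95.5%. It is not evidence for a missing visit term, and the documents do not establish that such variance exists.

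**The test eye may be fixed.** Section 4.1 describes the control solutions, in the plural, as going to one eye over the course of the study and the test solution to the other. This leans towards a fixed test eye, where the loss is smaller. Section 5.1 speaks of each period and leaves the matter open.

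**Large losses need extreme inputs.** At visit variance 200, twice the residual, the SE ratio reaches 1.36 (stacked, re-drawn). Nothing in the documents supports a value that high. Under another set of assumed variance shares (subject 0.3, eye 0.1, visit 0.1–0.3, residual the rest), the excess was 4–17% re-drawn and 0–4% fixed.

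**Other text might cover the gap.** Section 14.1 suggests using all scores but does not say how repeats enter. CLDEQ-8 may be a covariate, but its visit is not named. After Visit 1 it asks about average-day comfort in washout lenses, so it could absorb only part of a shared visit effect.

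**It is a pilot.** No margin or power claim depends on these intervals, and the raw data would still allow the paired SD to be computed later. These points stand and limit the weight of the concern.

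**Conclusion.** The gap in specification holds on the text alone: no visit index, no visit-specific term common to both eyes, and no rule for the repeated scores. Its numerical effect rests wholly on assumed variances. For visit variance between half and all of the residual, and no subject-by-solution variance, the planned SE is about 8–16% too large relative to the better model if the test eye is re-drawn and 2–12% if it is fixed. Coverage is at or slightly above nominal. With no visit variance there is no loss. The error from this omission alone is on the conservative side for interval width, and it inflates the variance a planner would take from the fit. Since the study is exploratory, this is a cheap improvement and not a threat to its conclusions.

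**What to change.** In Section 14.5:

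- Index the response by period and visit. Keep Visits 2 and 4 in the likelihood, with the 2-hour entry missing by design.
- Add visit within period as a fixed effect.
- Add a subject-by-visit random effect shared by both eyes (or a cross-eye residual covariance within visit), together with a subject-by-solution random effect. Subject-by-visit alone is not enough: with subject-by-solution variance 25–50 and visit variance 50–200, it gave coverage of 87.4–92.6% when stacked and re-drawn.
- Give a sensitivity analysis with only the present random effects, on the same stacked data.
- Report the SD of the within-visit test-minus-control difference at each time.

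Reconcile Sections 4.1 and 5.1 on whether the test eye is re-drawn for Period 2.

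The cost is plan wording and SAS code, with no new data or visits. There are two more variance parameters, and intervals may widen or narrow: across the assumed settings the planned SE was 0.77–1.40 times the SE with both terms. If the test eye is fixed, eye and subject-by-solution variance separate weakly. In simulation with 90 subjects and the Section 14.5 priors (Gibbs sampling in place of SAS Metropolis), mean posterior medians were 11.5–12.9 for a true eye variance of 20 and 55.7–59.6 for a true subject-by-solution variance of 50, while coverage stayed at 94.8–95.1%. That is a further reason to report the paired SD directly.

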2.3. Hypotheses

The test solution will be similar to the control solutions with respect to initial comfort at 1-min, 5-min, 45-min and 2 hours post-fit of pre-soaked lenses.

This is a pilot study and all the hypothesis are exploratory in nature.

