4.3. Enrollment Target and Study Duration

A total of up to 120 subjects (i.e. 40 per study lens) will be enrolled (informed consent signed). The goal is for a sample size of approximately 90 subjects (i.e. 30 per study lens) after subjects who withdraw or are lost to follow-up.

The Investigator is responsible for ensuring that all subjects entering the study conform to subject selection criteria. The number of subjects targeted for randomization and completion are as follows:

The number of subjects targeted for randomization and completion are as follows:

Table 1: Target number of subjects by arm and site

	ACUVUE 2	OASYS	Vita	Total
Randomization	36	36	36	108
Completion	30	30	30	90
Number of sites				4
Number of subjects/site	25-35	25-35	25-35	90-120
Min-Max				

The study will last approximately four weeks for each subject and the entire study duration will be approximately 4 months and include a 2-month enrollment period.

Once the informed consent has been signed the subject will be considered enrolled.

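### Does the false prior-mean identity behind the inverse-Wishart scale in section 14.5 call for a change to the primary analysis?

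*Combined protocol and SAP*

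**What the plan says.** In the primary model (section 14.5) each vector of four comfort scores (1, 5, 45 and 120 minutes) is multivariate normal. Its covariance Σ "is a 4×4 variance-covariance matrix". Random effects for site, subject and eye are modelled separately, so Σ is what remains after those effects and the fixed effects.

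The prior listed is "inverse Wishart $IW(R, 4)$ for" this matrix. R is fixed by setting S equal to E[Σ] and to 4R, so R = S/4, "where S is the sample variance-covariance matrix of the" score vectors. The section introduces all its priors with this description: "Non-informative prior distributions will be used for the coefficients in the models as well as for the error terms". It does not name the inverse-Wishart parametrisation and gives no other rule for R.

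Three other places bear on the size of the issue. The Time and Events table (section 7.1) schedules the "120-minute follow-up VAS comfort" at Visits 3 and 5 only. Section 4.3 states: "The goal is for a sample size of approximately 90 subjects". Section 2.3 states: "This is a pilot study and all the hypothesis are exploratory in nature".

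**The concern.** The sentence that fixes R rests on a moment that IW(R, 4) does not have. A programmer who checks the prior mean of Σ finds that it is infinite, so the prior is not centred on S as the text implies. There is a second mismatch. S is the total covariance of the raw scores, with site, subject, eye and solution differences included, whereas Σ is only the residual part. S also comes from the trial's own outcomes, which sits awkwardly with calling the prior non-informative.

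Section 14.5 is the only specification of the primary analysis. If the wrong rule produced a prior that was badly scaled or strong, the credible intervals for the test-versus-control differences would be too wide or too narrow. If the rule could not be carried out, two analysts might use different priors.

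**Working it through.** **1. The plan's own figure, E[Σ] = 4R.** Inputs from section 14.5: dimension p = 4, degrees of freedom ν = 4.

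- The prior is proper if ν > p − 1: 4 > 3, so it is proper.
- The mean is R/(ν − p − 1) and exists only if ν > p + 1: 4 > 5 fails (ν − p − 1 = −1). There is no finite mean.
- A mean of 4R would need 1/(ν − 5) = 4, that is ν = 5.25.
- Other readings do not rescue it. A Wishart with scale R and 4 degrees of freedom on Σ⁻¹ gives E[Σ⁻¹] = 4R, and E[Σ] is still not finite. A shifted-degrees-of-freedom form has ν = 4 + 4 − 1 = 7 and mean R/2. Only a Wishart(R, 4) has mean 4R.
- Simulation agrees. With R = S/4, the running mean of Σ₁₁/S₁₁ is about 92, 3,815, 25,476 and 140,373 at 10³, 10⁴, 10⁵ and 10⁶ draws and does not settle. The simulated Wishart(R, 4) mean divided by R is about 4.00.

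The figure is not reproduced; the identity is wrong.

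**2. The prior that R = S/4 actually gives.** Each variance is marginally inverse gamma with shape (ν − p + 1)/2 = 1/2 and scale R_jj/2 = S_jj/8. Its median is 0.55 S_jj and its central 95% range is 0.05 to 255 times S_jj. This is a very weak prior on the right order of magnitude.

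**3. Effect on interval width.** Take the mean and random effects as known and S proportional to Σ. With n vectors, the posterior mean of Σ, in units of the residual Σ, is (R/Σ + n)/(n + ν − 5). Interval width scales with its square root. The comparator is ν = 6 with R = Σ, which gives (1 + n)/(n + 1) = 1.

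- n: 90 completers × 2 eyes × 2 visits with a 120-minute score = 360. One vector per eye, 90 × 2 = 180, is a low bound.
- S/Σ is not in the documents. It is assumed to be 1 to 4, so R/Σ = 0.25 to 1.

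| S/Σ | n = 180 | n = 360 |
|---|---|---|
| 1 | √(180.25/179) = +0.35% | √(360.25/359) = +0.17% |
| 2 | √(180.5/179) = +0.42% | √(360.5/359) = +0.21% |
| 4 | √(181/179) = +0.56% | √(361/359) = +0.28% |

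The prior scale supplies between 0.25/360.25 = 0.07% and 1/181 = 0.55% of the posterior scale. That is also the extent to which the trial's scores are used twice.

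**4. Where the difference comes from.** Moving only the degrees of freedom from 6 to 4, with R = Σ, gives √(181/179) = +0.56% and √(361/359) = +0.28%. Changing only the scale from Σ to S/4, with 6 degrees of freedom, gives √(180.25/181) = −0.2% at S/Σ = 1 and n = 180, and exactly 0 at S/Σ = 4. The widening is therefore the price of the vaguer prior. The wrong scale rule contributes nothing or a slight narrowing.

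**5. Check in a hierarchical model.** A Gibbs run of a simplified hierarchical model (90 subjects, 360 vectors, assumed variances) gave a posterior SD for a solution contrast of 1.822 as the plan is written and 1.819 with the alternative prior. The ratio is 1.822/1.819 = 1.0016, a difference between 0.1% and 0.2%.

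**The case for a change.** The strongest case for a change is that the primary model should be specified correctly as well as harmlessly, and that a correction costs one sentence. An analyst who notices the false identity might try to honour its intent by centring the precision on S⁻¹. With 4 degrees of freedom that needs R = 4S, 16 times the scale of S/4. Using 6 degrees of freedom would make E[Σ] = R true, and taking R from a masked residual fit would remove the total-versus-residual mismatch.

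The error in the identity stands, and so does the mismatch between S and Σ. The rest does not carry the case. The text itself yields R = S/4 with 4 degrees of freedom and nowhere states R = 4S, so an analyst who follows it has one prior to code. The replacement is more informative than the prior it replaces. It again takes its scale from the trial's own scores, and a fit without solution codes leaves any solution difference in the residual or eye terms. Nor does a literal repair clearly help. IW(S, 6) with the total covariance makes the identity true, but at S/Σ = 4 and n = 180 its intervals are √(184/181) = +0.83% wider than the comparator, against +0.56% as printed. The objection to the word non-informative is one of labelling, since 4 degrees of freedom is nearly as vague as this family allows.

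**Conclusion.** The stated prior mean is wrong: a Wishart moment appears to have been carried over to an inverse Wishart. The rule it justifies is nonetheless computable, proper and very weak, and following section 14.5 as written gives a sound analysis. The alternative prior would change interval width by roughly 0.1 to 0.6%, and that change reflects the choice of degrees of freedom. An analyst can code R = S/4 with 4 degrees of freedom and treat it as a chosen weak scale.

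The percentages rest on a known-mean approximation, on S proportional to Σ with a ratio of 1 to 4, and on width depending on Σ alone. The eye-level variance may also enter a between-eye contrast, which would dilute the effect. The counts leave out the partly observed vectors from Visits 2 and 4 (90 × 2 × 2 = 360 more); using them would shrink the effect further at the first three time points. For an exploratory pilot with no power calculation (section 14.2), no conclusion depends on this, and no change to the plan follows.
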